## 14.2. SECONDARY CRITERIA

All secondary analyses will be performed on the FAS.

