### **Study objectives**

The primary objective of the study is to assess the efficacy of F373280 on the maintenance of sinus rhythm after direct ECV in patients with persistent AF and chronic heart failure.

The secondary objectives of the study are to assess:

- the efficacy of F373280 on the efficiency of direct ECV
- the effect of F373280 on echocardiographic parameters
- the safety and tolerability of F373280

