### **Study treatment**

After a 1 to 4-week run-in period, patients are randomised into one of the following treatment groups: F373280 1g or placebo 1g for 24 weeks. The treatment starts 4 weeks before ECV and ECV is performed in patients with no spontaneous cardioversion and with INR levels stabilized as mentioned in the protocol. The follow-up is of 20 weeks after a successful ECV (at visit 3 – cardioversion visit) or after a spontaneous CV.

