### **Sample size**

Assuming an AF recurrence rate of 85% under placebo and 65% under active group, i.e. a clinically relevant difference  $\Delta$  of 20%, a sample size of 64 assessable patients per group is

required, using a log-rank test of survival curves with a 80 % power and a 5 % two-sided significance level. According to the previous assumptions and assuming a rate of not assessable patients of 15%, a minimum of 76 patients have to be randomised per group. Due to low recruitment, it was decided to stop prematurely the study. 135 patients were finally randomised (instead of 152 initially planned).

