**V5 et V8 were cancelled in the amendment PA05**

## 7. ANALYSIS SETS

The following analysis sets will be defined:

- **The Screened patients Set** which consists of all patients who have signed an informed consent,
- **The Randomised Patients Set** which consists of all patients who have signed an informed consent, and are assigned a treatment number,
- **The Safety Set** composed of all randomised patients having taken at least one dose of the study treatment. This set will be used to perform analyses of Safety.
- **The Full Analysis Set (FAS)** composed of all randomised patients having received at least one dose of the study treatment and with a successful cardioversion observed at visit 3. A successful cardioversion will be defined as either spontaneous cardioversion before V3 or successful ECV performed at V3 (early relapse within the observation period after ECV will be considered as non successful). This set will be used to perform analyses of Efficacy.
- **The Per Protocol Set (PP)** which is the subset of the Full Analysis Set composed of all FAS patients without any major protocol deviation or other source of bias for primary criteria analyses. This set will be used to perform the supportive analysis of the primary efficacy criterion.

Patients from Randomised Patients Set, Safety Set, Full Analysis Set or PP set will be analysed as treated (*ie* as treatment actually received at the randomisation). In case of error of treatment dispensation during the study period, the assignment of patient treatment group will be discussed during the data review meeting.

Randomised patients not treated will be analysed as randomised (*ie* as treatment allocated at the randomisation).

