## 14. ANALYSIS OF EFFICACY

Unless otherwise specified, the efficacy analysis will be performed on the FAS. Baseline values will be the latest value measured before the first study drug intake.

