#### ***14.2.5.4. Number and duration of hospitalizations***

Hospitalizations for cardiovascular events will be characterised by:

- Hospitalization for AF treatment
- Hospitalization for worsening of heart failure
- Hospitalization for myocardial infarction

The number of hospitalizations (for cardiovascular events, for thromboembolic stroke and for all causes) will be described by treatment group and compared using Cochran-Mantel-Haenszel test stratified by country.

The duration of hospitalizations for cardiovascular events, for thromboembolic stroke and for any cause will be described by treatment group and compared using a non-parametric analysis of covariance (based on ranks) adjusted for country.

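### Hospitalisations are compared between arms only on the FAS, which is selected on cardioversion at V3, so admissions of treated patients who did not convert are missing from that comparison

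*SAP*

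**What the plan says.** Section 14 sets a default: "Unless otherwise specified, the efficacy analysis will be performed on the FAS". Section 14.2 then states, for the secondary criteria, "All secondary analyses will be performed on the FAS".

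Section 14.2.5.4 covers hospitalisations for cardiovascular events (AF treatment, worsening heart failure, myocardial infarction), for thromboembolic stroke and for all causes. Their number is to be "compared using Cochran-Mantel-Haenszel test stratified by country" and their duration "compared using a non-parametric analysis of covariance (based on ranks) adjusted for country". The section names no other analysis set and no counting window. Appendix 5 lists one table for number and one for duration, both on the FAS. Section 18 adds no hospitalisation analysis on another set.

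Section 7 restricts the FAS to treated patients "with a successful cardioversion observed at visit 3". Spontaneous conversion before V3 qualifies, and early relapse after ECV counts as failure. Under Study treatment in Section 6, dosing begins 4 weeks before ECV. One of the secondary objectives is "the efficacy of F373280 on the efficiency of direct ECV".

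**The concern.** The FAS suits the recurrence endpoints, because a patient must be in sinus rhythm before AF can recur. Admission for stroke, worsening heart failure or any cause has no such precondition. Since 14.2.5.4 gives no window, a converter's admission in the first 4 weeks can count, while a non-converter's admission in the same weeks cannot.

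Two things follow. Admissions of treated patients outside the FAS are absent from the only planned between-arm comparison of this outcome. In addition, FAS membership is settled after about 4 weeks on treatment, by an event the drug is meant to influence. If it does influence it, the two FAS arms contain differently selected patients, and the tables cannot be read as a comparison of the treatments as allocated.

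**Working it through.** **Inputs.** The SAP gives no figure on this point: neither the number of treated patients outside the FAS nor how long non-converters are observed. It does state that "135 patients were finally randomised", which is an upper bound for the number treated. All other inputs below are assumptions. The sample-size figures in Section 6 can be reproduced (hazard ratio ln 0.35 / ln 0.15 = 0.553; 95 events by Freedman's formula; 95 / 0.75 / 2 = 63.3, so 64 per group; 64 / 0.85 = 75.3, so 76), but nothing here depends on them.

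**Patients outside the FAS.** Assume a proportion p of 5-30%: 0.05 × 135 = 6.75 and 0.30 × 135 = 40.5, so about 7 to 41 patients.

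**Share of admissions omitted.** With equal weekly admission rates, and t the fraction of 24 weeks for which non-converters are observed, the share is p·t / (p·t + 1 − p). If they are observed only to V3, t = 4/24:

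- p = 5%: 0.0083 / (0.0083 + 0.95) = 0.9%
- p = 30%: 0.05 / (0.05 + 0.70) = 6.7%

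If they were observed for all 24 weeks (t = 1), the share would equal p, that is 5-30%.

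**Bias from selection.** Suppose the drug has no effect on admission and only adds converters. Let conversion be c0 on placebo and c1 on drug. Let admission risk be r1 = 15% in patients who convert on either treatment and r2 in those who convert only on drug. The FAS difference is then (c1 − c0) / c1 × (r2 − r1):

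| c0 v c1 | r2 = 30% | r2 = 45% |
|---|---|---|
| equal | 0 | 0 |
| 80% v 85% | 0.9 points | 1.8 points |
| 75% v 85% | 1.8 points | 3.5 points |
| 70% v 90% | 3.3 points | 6.7 points |

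For scale, take 67.5 patients per arm, 75% v 85% and r2 = 30%. The standard error of the risk difference is √(0.15 × 0.85 / 50.6 + 0.168 × 0.832 / 57.4) = 7.0 points, so the bias is 0.25 standard errors. In the largest case it is 6.7 / 7.4 = 0.90.

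**The error can also go the other way.** Take conversion of 75% on placebo and 90% on drug, with admission risk 15% in converters and 35% in non-converters in both arms. The FAS shows 15% v 15%. All treated patients show 0.75 × 15 + 0.25 × 35 = 20.0% v 0.90 × 15 + 0.10 × 35 = 17.0%. A benefit acting through conversion would not be seen on the FAS.

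**Why a Safety Set table needs observation time.** Take 20% non-converters in one arm and 10% in the other, observed 4 weeks, with everyone else observed 24 weeks. Mean observation is 0.8 × 24 + 0.2 × 4 = 20.0 v 0.9 × 24 + 0.1 × 4 = 22.0 weeks. At the same weekly rate, raw counts differ by a ratio of 20.0 / 22.0 = 0.91, while the rate per patient-week gives 1.00.

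**The case against.** The trial asks about maintenance of sinus rhythm, and Section 6 defines follow-up in those terms: "The follow-up is of 20 weeks after a successful ECV", or after a spontaneous conversion. Admissions among converted patients are a coherent exploratory question within that design. Section 8 makes every result except the primary test exploratory. Section 17.2 tabulates treatment-emergent events of all treated patients by seriousness and arm, and lists each SAE. The bias also needs a conversion difference and a risk difference that the SAP does not give. The Safety Set is not strictly the randomised comparison either, since it requires a dose and is analysed as treated.

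Most of this stands, and it keeps the point small. It does not remove it. The safety outputs are descriptive and do not separate admissions from other serious events. The SAE listing gives the duration of the event, not the length of stay. No output shows number or length of admissions by arm for all treated patients. The Safety Set, though imperfect, is not selected on V3.

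A reader might go further than the document allows in four ways:

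- *The FAS comparison is biased.* That holds only if the drug changes who converts and those patients differ in admission risk. Neither is known.
- *Up to 30% of admissions are lost.* That figure needs 24 weeks of observation in non-converters, which the SAP nowhere supports.
- *Sections 14 and 14.2 contradict each other.* They do not. One sets a default and the other names the same set.
- *The Cochran-Mantel-Haenszel and rank tests are wrong and must be replaced by count models.* The point concerns the population, not those tests. With at most 135 patients and probably few stroke admissions, such models could be unstable.

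**Conclusion.** The point holds as a low-cost improvement, not as an error that threatens the trial. The only between-arm comparison of hospitalisations is confined to a set chosen by an outcome after about 4 weeks of treatment, although the outcome itself does not require conversion. If non-converters are observed only to V3, about 1-7% of admissions are omitted, assuming 5-30% of patients outside the FAS and equal weekly rates. The selection bias is zero if conversion is unaffected by the drug and at most about 0.9 standard errors in the assumed cases. Its direction cannot be predicted. The primary analysis is untouched. How long non-converters are followed, and whether their admissions are recorded after V3, may be settled in the protocol, which was not available.

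**What to change.** - In 14.2.5.4 and Appendix 5, add the number and duration of hospitalisations by arm on the Safety Set, from first study drug intake to the last day of observation.
- Show observation time by arm, with admissions and hospital days per patient-week.
- State whether the planned stay for ECV at V3 counts. The flow-chart leaves outpatient or inpatient ECV to the centre's practice.
- Keep the FAS tables and their existing tests as supplementary.
- Reword the sentence in 14.2 to allow the exception, for instance: *Secondary criteria are analysed on the FAS except where a subsection names another set.*
- Optionally, fit a rate model with observation time as offset, for all-cause admissions only.

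The cost is a few lines of SAP text and two or three tables, and the change can be made before code release. The added rates remain limited if stopping is related to admission risk, or if admissions of non-converters are not collected after they leave.

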### 14.2.1. Numbers of Atrial Fibrillation/ Flutter Episodes in the first week following V3

The total number of AF/flutter episodes (symptomatic or not, lasting for at least 10 minutes or less than 10 minutes) during the 7-day holter monitoring will be described by treatment group and compared by the Cochran-Mantel-Haenszel test adjusted by country.

#### **14.2.2. Duration of Atrial Fibrillation/ Flutter Episodes in the first week following V3**

The duration of all AF/flutter episodes during the 7-day holter monitoring will be described by treatment group and compared using a non-parametric analysis of covariance (based on ranks) adjusted for country.

#### **14.2.3. Time to first AF recurrence / flutter emergence less than 10 minutes during TTEM period**

The time to the first AF recurrence / flutter emergence less than 10 minutes will be analysed as the primary analysis.

#### **14.2.4. Time to first symptomatic AF recurrence / flutter emergence during TTEM period**

The time to the first symptomatic AF recurrence / flutter emergence\* will be analysed as the primary analysis.

*\* Symptomatic AF recurrence/Flutter emergence will be defined as AF recurrence/Flutter emergence associated with at least one symptom (palpitation, fatigue, dizziness, dyspnea, chest pain and anxiety) in EHRA evaluation.*

#### **14.2.5. Clinical parameters evaluation**

##### **14.2.5.1. EHRA score**

AF related symptoms were evaluated by the EHRA (European Heart Rhythm Association) score. The following items "during presumed arrhythmia episodes" are checked to determine the score: palpitation, fatigue, dizziness, dyspnea, chest pain and anxiety.

Classification of AF-related symptoms (EHRA score) are as follows:

- EHRA I - 'No symptoms'

- EHRA II - 'Mild symptoms'; normal daily activity not affected
- EHRA III - 'Severe symptoms'; normal daily activity affected
- EHRA IV - 'Disabling symptoms'; normal daily activity discontinued

The maximum EHRA score will be described by treatment group and analysed using the Cochran-Mantel-Haenszel statistics (row mean scores) stratified by country effect using modified ridit scores.

In addition to this score, the frequency of symptoms will be classified in three groups, namely occasionally (less than once per month), intermediate (1/month to almost daily) and frequent at least daily, and will be described by treatment group.

#### ***14.2.5.2. Presumed arrhythmia***

A presumed arrhythmia will be defined as an EHRA score equal to II, III or IV.

The frequency of presumed arrhythmia (will be described by treatment group).

#### ***14.2.5.3. Recurrence of symptomatic AF***

The number of recurrences of symptomatic AF consists of the number of AF recurrences during TTEM period associated with at least one symptom (palpitation, fatigue, dizziness, dyspnea, chest pain and anxiety) in EHRA evaluation.

The number of recurrence of symptomatic AF will be described by treatment group and compared using the Cochran-Mantel-Haenszel test stratified by country.

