### **Primary efficacy criterion**

The primary criterion is the time to first Atrial Fibrillation recurrence or Atrial Flutter emergence defined by the time to first episode of Atrial Fibrillation or atrial flutter lasting for at least 10 minutes during the follow up of 20 weeks after visit 3 (ECV visit).

The cardiac monitoring is performed using:

- A 7-day continuous ECG ambulatory recording (Holter ECG) between visit 3 (ECV visit) and visit 4 (week 5) in patients cardioverted to sinus rhythm.
- A Trans Telephonic ECG Monitoring (TTEM):

\* before protocol amendment PA05: with a daily transmission from week 6 to week 8; then every two days from week 9 to week 24, and at anytime in case of AF symptoms

\* after protocol amendment PA05: with one transmission per week from the day of visit 4 (end of week 5) to visit 9 (week 24).

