## STUDY FLOW-CHART (PROTOCOL VERSION 9 28/09/2016)

F373280 CA 201

Weeks	V1 W-4 to W-1	V2 D1	V3 W4 (28 -2D/+7 D)	V4 W5 (35 -2D/+7 D)	V6 W12 (84+/-7D)	V7 W16 (112+/-7D)	V9 W24 (168+/-7D)
Outpatient or Hospitalization (1)			X				
Informed consent	X						
Demographic characteristics	X						
Medico-surgical history	X						
Concomitant disease	X						
Concomitant treatment	X	X	X	X	X	X	X
Habits	X						
Global physical examination (body weight)	X	X	X		X	X	X
Echocardiography	X	X		X		X	
Eligibility criteria check	X	X					
Blood pressure, heart rate	X	X	X	X	X	X	X
12-Lead ECG Recording	X	X	X		X	X	X
INR					X		→ (2)
aPTT, TCT	X	X	X		X	X	X
Biochemistry	X						X
Haematology	X		X				X
Urinary pregnancy test			X				X
Red Blood Cell concentrations of DHA		X	X			X	X
Treatment number allocation			X			X	
IVRS/IWRS	X	X				X	
ECV (3)			X				
Drug administration							→
Adverse events recording		X	X	X	X	X	X
Holter ECG	↔ (4)		↔ (5)				
TTEM (6)							→

 Outpatient or hospitalization according to clinical practice of the centre (less or more than 24 hours) In case of VKA introduction: INR 2 to 3 times a week until stabilization, then weekly until the ECV, then every 4 weeks after ECV In patients with AF 24-hour Holter ECG 7-day Holter ECG TTEM: one transmission per week from the day of visit 4 (end of week 5) to visit 9 (week 24) and at any time in case of AF or atrial flutter symptoms.

TTEM once a week even in case of AF recurrence or atrial flutter emergence for at least 10 minutes.

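### Symptomatic recurrences and hospitalisations are compared as raw counts, with no allowance for how long each patient was followed (minor)

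*SAP*

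**What the plan says.** Section 14.2.5.3 defines the recurrence endpoint as "the number of AF recurrences during TTEM period associated with at least one symptom" and gives its analysis: "The number of recurrence of symptomatic AF will be described by treatment group and compared using the Cochran-Mantel-Haenszel test stratified by country". Section 14.2.5.4 reads: "The number of hospitalizations (for cardiovascular events, for thromboembolic stroke and for all causes) will be described by treatment group and compared using Cochran-Mantel-Haenszel", again stratified by country. Country is the only adjustment in either place. No rate, offset or follow-up term appears in these sections, in section 10 (missing data and drop-outs) or in section 18 (changes since the protocol).

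Four other parts of the SAP bear on this:

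- Section 7 admits to the FAS every treated patient with a successful cardioversion at V3. It sets no minimum follow-up afterwards.
- Section 14.1 censors patients who end treatment early, and section 14.2.4 analyses time to first symptomatic recurrence in the same way. The count endpoints have no counterpart.
- Section 6 gives two TTEM schedules. Before amendment PA05 it was "with a daily transmission from week 6 to week 8; then every two days from week 9 to week 24"; afterwards it was weekly. Both allow extra transmissions for symptoms; the flow-chart note for the weekly schedule adds "and at any time in case of AF or atrial flutter symptoms". The same note says "TTEM once a week even in case of AF recurrence", so on that schedule a first recurrence does not end the counting.
- Section 8 makes every test other than the primary one exploratory.

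**The concern.** A count accrues over time. If the analysis ignores how long each patient was observed, a patient who leaves early with no events is ranked with a completer who had none, although the first had far less opportunity to have any. If one arm loses more patients than the other, its counts fall for a reason unrelated to the drug's effect on the event rate, and the comparison favours that arm. These two results would be read as clinical support for the primary finding, so the direction of the distortion matters even though the tests are exploratory.

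**Working it through.** The SAP gives no figure for either count endpoint, so there is none to reproduce. Its only sample-size figure, 64 assessable patients per group for the primary log-rank test, follows from its assumptions: hazard ratio ln(0.35)/ln(0.15) = 0.553, 95 events by Freedman's formula, and 95/0.75 = 126.7 patients, or 64 per group. It serves below only as a realistic trial size.

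**1. Follow-up by visit reached** (visit weeks from the flow-chart; V3 at week 4, TTEM from week 5)

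| Last visit | Weeks since V3 | Completer's follow-up relative to this | TTEM weeks |
|---|---|---|---|
| V9 | 24 − 4 = 20 | 1 | 19 |
| V7 | 16 − 4 = 12 | 20/12 = 1.7 | 11 |
| V6 | 12 − 4 = 8 | 20/8 = 2.5 | 7 |
| V4 | 5 − 4 = 1 | 20/1 = 20 | 0 |

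**2. Effect on mean counts when the drug does nothing.** Assume the same constant event rate in both arms and leavers departing uniformly over the period, so that each contributes half the period on average. Mean follow-up is then 1 − 0.5d for withdrawal proportion d, and the ratio of mean counts is (1 − 0.5d₁)/(1 − 0.5d₀):

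- 15% v 15%: 0.925/0.925 = 1.00
- 20% v 10%: 0.90/0.95 = 0.95
- 30% v 10%: 0.85/0.95 = 0.89
- 40% v 10%: 0.80/0.95 = 0.84

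**3. Effect on the test.** Simulation with every input assumed: 64 per arm, four country strata, gamma-Poisson counts (mean 2, dispersion 1), leavers departing uniformly over 19 weeks, half the patients on a four-fold denser schedule with counts proportional to transmissions, 3000 runs. The test is the country-stratified CMH with modified ridit scores. Section 14.2.5.1 names those scores for EHRA; using them for the counts is an assumption.

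| Withdrawal, no true effect | Raw counts | Counts divided by exposure |
|---|---|---|
| 15% v 15% | 4.4% | 5.0% |
| 30% v 10% | 7.0% | 6.1% |
| 40% v 10% | 11.2% | 7.1% |
| 30% v 10%, one schedule only | 7.1% | 5.4% |

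The Monte Carlo standard error near 5% is √(0.05 × 0.95/3000) = 0.4 percentage points. The last row is closest to hospitalisations, on which the TTEM schedule has no bearing. A second simulation (115 patients, mean 0.05 events per transmission, 2000 runs) gave 8.5% for raw counts at 30% v 10% and 10% at 40% v 10%.

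**4. Schedule.** Before PA05: 3 × 7 = 21 daily transmissions plus 16 × 3.5 = 56 on alternate days, 77 in all. After PA05: (168 − 35)/7 = 19 intervals, so 19 to 20 transmissions. The ratio is 77/20 = 3.9 to 77/19 = 4.1. The effect is mainly on precision: at a true rate ratio of 0.6 with equal withdrawal, power was 34% for raw counts and 38% per unit of exposure with mixed schedules, against 44% and 45% with one schedule.

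**The case against.** The strongest reply is that little depends on these tests. They are exploratory under section 8. Section 14.2.4 already analyses the first symptomatic event with censoring. Section 12 tabulates withdrawals and visits by arm, and section 17.1 tabulates exposure by arm, so a reader could see unequal follow-up. All of this stands and sets the severity. It does not repair the count comparisons: hospitalisations have no time-to-event counterpart, and a table of withdrawals does not correct a p-value.

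A reader might also infer more than the SAP supports:

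- *That the four-fold schedule difference biases the recurrence comparison.* The schedule changed by amendment, not by arm, so randomisation should roughly balance it. Symptomatic patients could transmit at any time under both schedules, so detection of symptomatic episodes need not differ four-fold. The simulations that make counts proportional to transmissions are the extreme case. The figure of 77 is also a full-schedule count: the SAP does not say whether dense monitoring continued after a recurrence.
- *That the number of transmissions should be the denominator.* The total includes symptom-triggered transmissions, which depend on the outcome. With 115 patients, a rate ratio of 0.55 and 15% withdrawal per arm (all assumed), power for raw counts v counts per transmission was 42% v 47% if all detection was schedule-driven, 49% v 47% if half was symptom-driven, and 52% v 45% if all was.
- *That the schedule affects hospitalisation counts.* It does not; only follow-up time matters there.
- *That follow-up did differ several-fold between patients.* It can, as the visit table shows, but the SAP does not report how many left or when.

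**Conclusion.** The point holds as a minor one. Both count analyses ignore length of follow-up, while the SAP's time-to-event criteria allow for it. The consequence is conditional: with equal withdrawal the CMH test keeps its level; with unequal withdrawal it favours the arm that loses more patients. At an assumed 30% v 10%, a null effect appears as a ratio of mean counts of about 0.89, and the 5% test rejects about 7% to 8.5% of the time. These figures rest on assumed withdrawal rates, uniform leaving times, withdrawal unrelated to a patient's own event rate, and assumed count distributions; the SAP supplies none of these. The PA05 schedule change mainly adds noise to the recurrence count. The primary analysis is not affected.

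**What to change.** Replace the raw-count CMH comparisons in sections 14.2.5.3 and 14.2.5.4 with negative binomial regression on treatment and country, falling back to Poisson if events are few:

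- **Hospitalisations:** offset log(days followed), over the same window in which hospitalisations are counted.
- **Symptomatic recurrences:** offset log(days in the TTEM period), plus a before/after-PA05 term with a stated rule for patients whose monitoring spans the amendment. A patient who leaves before TTEM starts has no exposure and contributes nothing; the text should say so, because a raw count could record a zero.

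Do not use the total number of transmissions as the offset. Ranking counts divided by exposure is only a partial repair: it still rejected 6.1% and 7.1% under unequal withdrawal with mixed schedules. At the least, report events per patient-time by arm beside the CMH result.

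The cost is a few lines of SAP text and a standard model using visit and TTEM dates. The drawbacks are that the model may be unstable with few events, and that the offset assumes a roughly constant event rate and withdrawal unrelated to the patient's own rate.
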